# PPD

## 4.2 Analysis sets

### 4.2.1 Enrolled set

The Enrolled set (ENR) will consist of all patients with signed written informed consent (IC) and undergoing to study evaluations/procedures.

### 4.2.2 Randomized set

The Randomised set (RND) will consist of all patients in the ENR set who are randomized to the study, regardless of whether they receive IMP or not.

### 4.2.3 Safety set

The Safety set (SAF) will consist of all randomized patients who receive at least one dose of the IMP. SAF population will be analyzed according to the actual treatment received and will be used to present results on safety data.

### 4.2.4 Full Analysis set

The Full Analysis Set (FAS) will consist of all randomized patients who receive at least one dose of the IMP (either ladarixin or placebo). FAS population will be analyzed according to ITT principle, i.e. by treatment allocation regardless happening of intercurrent events (treatment policy strategy). The FAS population will be used for the primary analyses of the study and to present results on efficacy data.

## 4.3 Primary estimand

Considering the premature closure of the study, the originally planned treatment policy strategy and estimand definition is not applicable. Summary analysis will be performed, descriptive in nature.

## 4.4 Usage of analysis sets

The usage of the analysis sets (see previous section) for the creation of tables and figures are illustrated in Table 2. Unless otherwise specified, all listings will be done for RND set. All listings will have planned and actual treatment names included, as well as the flag(s) of the analysis set(s) used to analyses the information of the listing (according to the Table 2).

Table 2: Usage of analysis set

Analysis	ENR	RND	FAS	SAF
Subject enrolment and disposition	X			
Protocol violations		X		
Study discontinuations		X		
Permanent treatment discontinuation criteria		X		

# PPD

Patient phone calls		X		
Demographics and baseline characteristics			X	
Medical or surgical history and/or Concomitant Diseases			X	X
Prior and concomitant medications			X	X
Other baseline characteristics			X	
Compliance to IMP				X
Exposure to IMP				X
Analysis of primary efficacy endpoint			X	
Analysis of secondary efficacy endpoints			X	
MMTT over the study			X	
Analysis of CCI			X	
Adverse events				X
Clinical laboratory evaluation				X
Vital signs				X
ECGs				X
Pregnancy test over the study				X

## 4.5 Sub-group analyses

Considering the premature closure of the study and the limited sample size compared to the originally expected, the analysis of the primary endpoint in pre-defined subgroups (by age, sex, race, BMI, Human Leukocyte Antigen Complex – HLA, CCI, site geographic region) will not be performed.

## 4.6 Interim analyses

No formal interim analysis is planned for the study.

## 4.7 Handling of missing and incomplete data

The number of patients with missing data will be presented under the “Missing” category, if present. Missing values will be included in the denominator count when computing percentages. Instead, only the non-missing values will be evaluated for computing summary statistics for continuous endpoint. Any exception will be clarified as a note.

## 4.8 Changes in the planned analysis

Due to the company decision to stop the enrolment, fewer patients compared to the originally planned will be available for the analysis. Thus, the following changes were implemented:

- one single final analysis is planned after DB lock;

# PPD

- no formal hypothesis testing will be performed;
- all analyses will be descriptive in nature;
- no advanced analytical methods will be applied, specifically:
  - Primary endpoint no more analyzed by means of logistic regression model: comparison between treatment arms performed by means of a Chi-square test at each time point.
  - No multiple imputation approaches to manage potential missing data;
- no sensitivity analyses will be performed;
- no sub-group analyses will be performed;

## 4.9 Blind Data Review Meeting

A Blind Data Review Meeting (BDRM) will be held before the database lock and unblinding of the data. Any other details will be provided in the BDRM Report.

## 4.10 Software

All statistical analyses and data processing will be performed using Statistical Analysis Systems (SAS®) Software (release 9.4) on a Windows 10 operating system.

CGM data at patient level will be processed using *cgmanalysis* package [4] in R version 3.6.1 (or later) before performing statistical analysis.

## 5. Evaluation of Demographic and Baseline Characteristics

### 5.1 Subject enrolment and disposition

All presentations for subject disposition will be by treatment group, and overall.

For describing the subject disposition, the following populations will be summarized:

- Subjects enrolled (overall);
- Subjects enrolled but not randomized and reasons for non-allocation (overall);
- Subjects randomized;
- Subjects in each analysis set (FAS, SAF) and reasons for exclusion;

For the overall report, the percentage denominator will be the number of ENR subjects. For the “by treatment group” calculations, the percentage denominator will be the number of randomized subjects within each arm.

For the second bullet point, the following information will be listed as well:

- Reason for discontinuation. If reason for discontinuation = “Inclusion Criteria not met / Exclusion Criteria met” the following information will be listed:

# PPD

- Specification about Inclusion/Exclusion criteria not met/met
- Corresponding Parameters, whether a threshold level of a laboratory/ECG parameter is expected to meet the criterion (Inclusion criteria #3 and #5, Exclusion criteria #2, #3, #4, #5)
- Results of corresponding parameter (for example, both C-peptide values)

Listings will be provided based on ENR set.

## 5.2 Protocol violations

All the protocol violations will be discussed case by case before unblinding of the treatment code with the clinical team during the BDRM and described in the BDRM Report.

Number of occurrences and of subjects with at least one major and minor protocol violations will be summarized for each treatment.

## 5.3 Permanent treatment discontinuation criteria

A summary table showing at each available time point the number and percentages of subjects who discontinued the study treatment along with the discontinuation criteria will be produced by treatment group. The number of patients still under treatment of discontinuing at the specific visit will be used as denominator for percentages.

## 5.4 Patient phone calls

A summary table showing at each available time point the number and percentages of subjects who were contacted by phone call and who needed/not needed an adjustment in the insulin regimen will be produced by treatment group. The number of all patients (including subjects that have discontinued IMP but still in the study) at the specific visit will be used as denominator for percentages.

## 5.5 Study discontinuations

The following information will be summarized for the randomized patients by treatment and overall:

- Trial completers;
- Number of subjects who completed each planned visit.
- Subjects who discontinued the IMP and reasons (taken from EOT form)
  - Subjects who discontinued the IMP but complete the study
  - Subjects who discontinued the IMP and discontinued the trial prematurely
- Subjects who discontinued the trial prematurely (and reason);

# PPD

- Broken randomization code (and reason).

## 5.6 Demographics and baseline characteristics

The baseline demographic characteristics will be summarized by treatment and overall, by means of descriptive statistics. No statistical testing will be carried out for demographic or other baseline characteristics.

The following demographic and baseline characteristics will be reported for this study:

- Geographic region of the site (EU, US, Other)
- Demography
  - Age (years)
  - Sex (Male, Female)
  - If female, potential childbearing (Yes, No)
  - Race (White, Black or African American, Asian, American Indian or Alaska Native, Native Hawaiian or other Pacific Islander, Other)
  - Ethnicity (Hispanic or Latino, Not Hispanic or Latino)
- Pregnancy test result (Positive or Negative), if appropriate
- T1D diagnosis
  - Diagnosis of T1D confirmed (Yes, No)
  - Time from T1D diagnosis to inform consent (days)
  - Time from first insulin administration to first IMP administration (days). The following formula will be used: date of first IMP administration – date of first insulin administration.
- BMI (BMI≤25kg/m^2 vs 25kg/m^2<BMI≤30kg/m^2 vs BMI>30kg/m^2)

## 5.7 Medical or Surgical History and/or Concomitant Diseases

A disease is considered as medical/surgical history if it is ended before screening visit.

A disease is considered as concomitant disease if it is ongoing at screening visit.

Medical history and concomitant diseases will be coded using Medical Dictionary for regulatory activities (MedDRA) dictionary and frequency distributions and percentages will be summarized by treatment, by System Organ Class (SOC), and Preferred Term (PT).

Medical history and concomitant diseases will be analyzed separately. Frequency distributions and percentages by treatment will be given for both SOC and PT by subject. Subjects experiencing more than one past/concomitant disease event will be counted only once within each SOC and PT.

## 5.8 Prior and concomitant medications

Medications will be coded using World Health Organization Drug Dictionary (WHO DD).

# PPD

Prior medications are those which stop prior to the date of informed consent. Concomitant medications are those which:

- start prior to, on or after the date of informed consent and start no later than date of study completion or discontinuation, and
- end on or after the date of informed consent or are ongoing at the study completion or discontinuation.

In case of missing or incomplete dates/times not directly allowing allocation to any of the two categories of medications, a worst-case allocation will be done according to the available parts of the start and the end dates (see Table 6). The medication will be allocated to the first category allowed by the available data, according to the following order:

- concomitant medication;
- prior medication.

Prior and concomitant medications will be summarized separately. Frequency distributions and percentages by treatment will be given by Anatomical Main Group (1st level of the Anatomical Therapeutic Chemical (ATC) classification), Chemical Subgroup (4th level of the ATC classification) and Preferred Name.

Subjects experiencing more than one medication classified in the same category (prior medications or concomitant medications) within the same anatomical main group, chemical subgroup and preferred name will be counted only once.

## 5.9 Other baseline characteristics

### 5.9.1 Fasting C-Peptide

Summary statistics by treatment of fasting C-Peptide (nmol/L) at baseline will be provided. In case of repetition of fasting C-Peptide evaluation (according to protocol), the repeated assessment will be considered as the only evaluation.

### 5.9.2 Auto-Antibodies

Auto-antibodies (anti-GAD; IAA, if obtained within 10 days of the onset of insulin therapy; IA-2 antibody; ZnT8) results to confirm T1D diagnosis and of fasting C-peptide will be descriptively summarized. In case of repetition of evaluation (according to protocol), the repeated value will be considered as the only evaluation value.

### 5.9.3 HLA DR-DQ haplotypes

HLA DR-DQ haplotypes at baseline will be listed only.

# PPD

## 6. Evaluation of Treatment Compliance and Exposure

### 6.1 Compliance to study treatment regimen

Descriptive analyses of the following parameters will be presented by treatment group for each cycle and during the entire treatment period:

- from IMP dispensation form
  - number of capsules dispensed;
- from IMP accountability form
  - number of returned blisters;
  - number of capsules taken;
  - number of returned unused capsules;
  - IMP intake compliance, ON -treatment period compliance (only by cycle);

Patients are instructed to receive study treatment (either ladarixin or placebo) as follows:

- 400 mg b.i.d (2 capsules at each administration, twice per day);
- for 13 cycles, each lasting 28 days;
- each cycle is composed by 14 consecutive days on-treatment and 14 consecutive days off-treatment.

Calculation of compliance to treatment regimen must consider not only the amount of treatment intake, but also the correct alternation between period “ON” and period “OFF” and their duration. To assess the overall compliance to treatment regimen, the following 3 criteria will be taken into account:

- Compliance to IMP intake;
- Compliance to duration of period “ON” (period of the cycle when the patient is ON treatment);
- Compliance to duration of period “OFF” (period of the cycle when the patient is OFF treatment).

#### 6.1.1 IMP intake compliance

##### 6.1.1.1 Over the entire treatment period

IMP intake compliance over the entire treatment period will be calculated as follow:

$$\begin{aligned} \text{IMP intake compliance (\%)} \\ = \frac{\text{total n. of capsules taken during the treatment period}}{\text{total n. of capsules dispensed during the treatment period}} \times 100 \end{aligned}$$

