### 6.2. IMP DISPENSATION

The IMP will be dispensed quarterly only by the Pharmacist (or authorized designee at site).

The IMP will be dispensed via IRS as Patient Kits during the Randomization Visit and then during the Visits scheduled at the end of the 3rd (Week 11), 6th (Week 23) and 9th (Week 35) treatment cycles, after check of inclusion/exclusion criteria (at Randomization) and discontinuation criteria at the scheduled visits \* (see [Section 6.4.2](#)).

A total number of 13 Patient IMP Kits will be dispensed to each randomized subject as follows:

- at Randomization Visit dispensed 3 Patient Kits for the Cycles 1, 2 and 3
- at Week 11 Visit dispensed 3 Patient Kits for the Cycles 4, 5 and 6
- at Week 23 Visit dispensed 3 Patient Kits for the Cycles 7, 8 and 9
- at Week 35 Visit dispensed 4 Patient Kits for the Cycles 10, 11, 12 and 13

[\* Results of ALT/AST, bilirubin, creatinine, albumin, ECG readings and pregnancy results should be made available by local laboratory in time to allow Patient Kits dispensation as soon as possible during the visit. If this expedite timing cannot be achieved, Patient Kits might be delivered to patient named address by a selected courier (CRO to support shipment). Study drug dispensation will be performed as soon as possible after check of discontinuation criteria.]

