# PPD

where “*total number of capsules taken during the treatment period*” is the sum of number of capsules taken at each cycle (CRF IMP ACCOUNTABILITY form), while the “*total number of capsules dispensed during the treatment period*” is given by the number of dispensed kits (CRF IMP DISPENSATION form) considering that each kit contains 56 capsules.

For a complete treatment period over 13 cycles the dispensed number of capsules and the number of capsules the patient is expected to take is the same and is equal to 728.

For a cycle that is interrupted due to treatment discontinuation the expected #capsules may differ from the # dispensed as follows:

- If interrupted before the expected last intake, the expected # capsules will be derived as:

$$\begin{aligned} \text{Expected # capsules} &= 56 * \# \text{ completed } k \text{ cycles } (k = 1 \dots i - 1) \\ &+ 4 * (\text{Date treatment discont in Cycle } (i) - \text{Data start Cycle } (i) + 1) \end{aligned}$$

In the expected #capsules calculation, it is assumed that the discontinuation occurs after last daily intake.

- If interrupted after the expected last intake, the expected number of capsules will be:

$$\text{Expected # capsules} = 56 * \# \text{ completed } k \text{ cycles } (k = 1 \dots i - 1) + 56$$

IMP intake compliance over the entire treatment period will be summarized by treatment by means of summary statistics.

In addition, compliance to IMP over the entire treatment period will also be presented for the following categories: <80%, 80%-100% (excluded), 100%, >100%.

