## 6.1.1.2 By cycle

Compliance by cycle with respect to IMP intake will be assessed following the formula below:

$$\begin{aligned} \text{IMP intake compliance at cycle } (i) (\%) \\ &= \frac{\text{total number of capsules taken during the cycle}}{\text{total number of capsules dispensed during the cycle}} \times 100 \end{aligned}$$

If cycle (i) is completed, the dispensed number of capsules and the number of capsules the patient is expected to take is the same and is equal to 56.

If cycle (i) is interrupted due to treatment discontinuation:

- If interrupted before the expected last intake, the expected number of capsules will be derived as:

$$\begin{aligned} \text{Expected # of capsules} \\ &= 4 * (\text{Date treatment discont in Cycle } (i) - \text{Data start Cycle } (i) + 1) \\ &\bullet \text{ If interrupted after the expected last intake, the expected number of capsules will be 56} \end{aligned}$$

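### SAP 6.1.1 prints capsules dispensed as the intake-compliance denominator and never substitutes the expected count it derives for patients who stop treatment, so perfect intake can score below 80%

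*SAP*

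**What the plan says.** SAP 6.1.1.1 defines overall intake compliance as capsules taken over the "total n. of capsules dispensed during the treatment period". The denominator is "given by the number of dispensed kits (CRF IMP DISPENSATION form) considering that each kit contains 56 capsules". For a full 13-cycle course, the SAP says that the dispensed number and the number the patient is expected to take "is the same and is equal to 728".

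The same section continues: "For a cycle that is interrupted due to treatment discontinuation the expected #capsules may differ from the # dispensed as follows". It then gives an expected count: 56 per completed cycle plus 4 per day of the interrupted cycle, or plus 56 if the stop comes after that cycle's expected last intake. The text does not say where this count is used.

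SAP 6.1.1.2 repeats the pattern by cycle. The printed denominator is the "total number of capsules dispensed during the cycle", followed by an expected count for an interrupted cycle that is not placed in the formula.

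SAP 6.1.1.3 calls a patient globally compliant with intake if (a) overall compliance lies between 80% and 100% inclusive and (b), (c) limits on out-of-range cycles are met. Conditions (b) and (c) are checked only in patients who completed treatment. SAP 6.1.4 requires this flag, together with the ON-period and OFF-period flags, for overall regimen compliance.

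Protocol 6.2 dispenses in batches, beginning "at Randomization Visit dispensed 3 Patient Kits for the Cycles 1, 2 and 3", then three kits at Week 11, three at Week 23 and four at Week 35.

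**The concern.** Compliance is meant to show whether patients took the capsules they were due to take. If the denominator counts kits for cycles the patient never reached, stopping treatment is scored as poor intake. Criterion (a) is the only intake criterion applied to early stoppers, so the choice of denominator by itself can turn their intake flag, and with it the regimen flag in 6.1.4, from Y to N. Two programmers could read the section differently and report very different values for the same patient.

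**Working it through.** **Inputs.** 56 capsules per kit, one kit per cycle (SAP 6.1.1.1). Four capsules per day: "2 capsules at each administration, twice per day" (SAP 6.1). Fourteen ON-days per cycle. Kits dispensed 3, 3, 3 and 4 (Protocol 6.2).

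**The plan's own figure.** 13 × 56 = 728, and 4 × 14 × 13 = 728. The SAP's total is reproduced, and dispensed equals expected for a completed course.

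**Early stop, perfect intake.** For a stop after the last intake on ON-day *d* of cycle *i*:

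- taken = 56(*i* − 1) + 4*d*
- literal denominator = cumulative capsules dispensed: 168, 336, 504 or 728
- expected count = 56(*i* − 1) + 4*d*, so the score is 100% at every stopping day

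Example, cycle 1 day 10: taken = 40. Overall, literal: 40/168 = 23.8%. By cycle, literal: 40/56 = 71.4%. With the expected count: 40/40 = 100% for both.

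**All possible early-stop ON-days.** There are 13 × 14 − 1 = 181; the last day of cycle 13 is completion.

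| Stop in cycles | Dispensed | 80% of dispensed | Lowest literal score | ON-days below 80% |
|---|---|---|---|---|
| 1–3 | 168 | 134.4 | 4/168 = 2.4% | 33 of 42 |
| 4–6 | 336 | 268.8 | 172/336 = 51.2% | 25 of 42 |
| 7–9 | 504 | 403.2 | 340/504 = 67.5% | 16 of 42 |
| 10–13 | 728 | 582.4 | 508/728 = 69.8% | 19 of 55 |

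Total: 33 + 25 + 16 + 19 = 93 of 181 (51%) below 80%; 181 − 93 = 88 at 80% or above.

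**Around the dispensing visits.** The ON part of cycles 3, 6 and 9 is over by Weeks 11, 23 and 35.

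- Stopped at the check, no new kits released: 168/168, 336/336, 504/504 = 100%.
- Stopped just after new kits are in hand: 168/336 = 50.0%, 336/504 = 66.7%, 504/728 = 69.2%.

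**By cycle.** The denominator is one kit, so batch dispensing plays no part. The shortfall arises only because 56 is used where the expected count is 4*d*.

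**Comparison within SAP 6.1.** The ON-period measure divides by expected duration. For an interrupted cycle, 6.1.2.1 adds the same duration to the observed and expected totals, and 6.1.2.2 sets expected equal to observed. The OFF-period measure in 6.1.3.1 also adjusts its expected total for discontinuation. Only intake compliance lacks the link. The overall categories in 6.1.1.1 also include a class above 100%; with dispensed capsules as the denominator, that class could be filled only by accountability errors.

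**The case against.** The best reply is that the SAP already deals with early stopping. The expected count stands directly under each formula, has no evident use except as a denominator, and matches how the ON-period measure works. A careful programmer would probably use it. That is good evidence of intent, but it does not repair the text: both formulas print 'dispensed', 6.1.1.1 defines that term explicitly from kits, and nothing says it is to be replaced.

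A reader might also infer more than the documents support:

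- *That early stoppers in general are scored as grossly non-compliant.* Even on the literal formula, 88 of 181 stopping days score 80% or more. Protocol 6.2 and 7.3 check discontinuation criteria before kits are released at Weeks 11, 23 and 35, and a perfect-intake patient stopped there scores 100%. The day-10 example lies towards the bad end.
- *That batch dispensing explains the by-cycle figure.* It does not, and by-cycle values do not reach the intake flag for early stoppers.
- *That the distortion favours one arm.* This would need different discontinuation rates. The only figures given, from the earlier type 1 diabetes trial (Protocol 2.4.2 and 2.4.3), are one adverse-event treatment discontinuation in each group (1 of 50 ladarixin, 1 of 26 placebo), after three cycles only.

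Little depends on the result. SAP 4.2 defines no set by compliance, and SAP 4.8 makes all analyses descriptive. Treatment discontinuations with reasons (5.5), capsule counts (6.1), cycles started (6.1.5) and exposure (6.2) are reported separately, so a reader could tell stopping from poor intake.

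**Conclusion.** The formulas are wrong as written, because they conflict with the SAP's own derivation for discontinuers. Applied literally, a patient with perfect intake who stops between dispensing visits, or after new kits are in hand, can fall below 80% and be flagged non-compliant on criterion (a) alone. In the worked case the score is 24% overall and 71% for the cycle, against 100% with the expected count.

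The count of 93 in 181 assumes perfect intake, dispensing on schedule and a stop after the day's last intake, as the SAP itself assumes. It is a count of possible stopping days, not a forecast of how many patients are affected; the documents give no distribution of stopping times. The effect is confined to the descriptive compliance tables and the Y/N compliance flags. No efficacy or safety analysis set changes.

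**What to change.** In SAP 6.1.1.1 and 6.1.1.2, replace capsules dispensed in the denominator by the expected number of capsules, stating that this equals the dispensed number for completed cycles and follows the rule already given for interrupted ones. Add one sentence to 6.1.1.3 saying that its criteria use these values. This brings intake compliance into line with the ON-period formulas in 6.1.2. Keep the number of capsules dispensed as a separate descriptive item, as 6.1 already plans.

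The cost is two formula edits and one sentence, with no new data. The expected count is already defined in the text; the documents do not show whether it has been programmed, so the compliance program should be checked against the revised wording.
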